3.4.2. Analysis Window

The nominal visit as recorded on the CRF will be used when data are summarized by visit. Any data relating to unscheduled visits will not be assigned to a particular visit or time point and in general will not be included in summaries but will be listed in the listings. However, the following exceptions will be made:

- An unscheduled visit prior to the first dose of study drug may be included in the calculation of predose value, if applicable.
- For subjects who prematurely discontinue from the study, ET data will be summarized as a separate visit, labeled ‘Early Termination Visit.’
- For laboratory abnormalities, all postdose values (including scheduled and unscheduled visits) will be used to assess the maximum toxicity.
- For vitals assessments, all postdose values (including scheduled and unscheduled visits) will be used to assess maximum postdose and maximum postdose change.

3.4.3. Selection of Data in the Event of Multiple Records on the Same Day

Depending on the statistical analysis method, single values may be required for each day. For example, change from predose by visit usually requires a single value.

If multiple valid, non-missing numeric observations exist on a day, records will be chosen based on the following rules if a single value is needed:

- For predose, the last available record on or prior to the date and time of the first dose of study drug will be selected. If there are multiple records with the same time or no time recorded on the same day, average (arithmetic or geometric mean, as appropriate) will be used for the predose value.
- For postdose values:
 - The record closest to the nominal day for that visit will be selected.
 - If there are 2 records that are equidistant from the nominal day, the later record will be selected.
 - If there is more than 1 record on the selected day, the average will be taken, unless otherwise specified.
 - If multiple, valid, non-missing categorical observations exist on a day, records will be chosen based on the following rules if a single value is needed:

- For predose, the last available record on or prior to the date and time of the first dose of study drug will be selected. If there are multiple records with the same time or no time recorded on the same day, the value with the lowest severity will be selected (e.g., normal will be selected over abnormal for safety ECG findings).
- For postdose values, if there are multiple records with the same time or no time recorded on the same day, the most conservative value within the window will be selected (e.g., abnormal will be selected over normal for safety findings).

4. SUBJECT DISPOSITION

4.1. Subject Enrollment and Disposition

A summary of subject enrollment (randomization) and disposition will be provided by treatment sequence and overall. This summary will present the number of subjects randomized, and the number and percentage of subjects in each of the categories listed below. For the Safety Analysis Set category, the denominator for the percentage calculation will be the total number of subjects randomized for each column using All Randomized Analysis Set. For all other categories, the denominator for the percentage calculation will be the total number of subjects in the Safety Analysis Set for each column.

- Safety Analysis Set
- PK Analysis Set for each analyte
- Completed study drug
- Did not complete study drug with reason for premature discontinuation of study drug
- Completed the study
- Did not complete the study with reason for premature discontinuation of study

In addition, the total number of subjects who were enrolled and the number of subjects in each of the disposition categories listed above will be displayed in a flowchart.

The following by-subject listings will be provided by subject ID number in ascending order to support the above summary tables:

- Reasons for premature discontinuation of study drug or study

A by-subject listing of subject disposition including treatment sequence, date of the first dose of study drug, date of the last dose of study drug(s) (study days), study drug completion status, reason for study drug discontinuation, study completion status, reason for study discontinuation, and PK set status (indicating whether or not a subject is included in a PK analysis set) will be provided by subject ID number in ascending order.

4.2. Extent of Exposure

A subject's extent of exposure to study drug data will be generated from the study drug administration page in the eCRF. Exposure data will be listed.

4.3. Protocol Deviations

A by-subject listing will be provided for those subjects who violated at least 1 inclusion or exclusion criterion, regardless of whether they were exempted or not by the sponsor. The listing will present the entry criterion (or criteria if more than 1 violation) that subjects did not meet and related comments, if collected.

Protocol deviations occurring after subjects entered the study are documented during routine monitoring. Any deviations identified will be evaluated to determine if it justifies excluding the subjects from any analysis sets.

5. BASELINE CHARACTERISTICS

5.1. Demographics

Subject demographic variables (ie, age, sex, race, and ethnicity) will be summarized by treatment sequence and overall using descriptive statistics for continuous variables and using number and percentage of subjects for categorical variables. The summary of demographic data will be provided for the Safety Analysis Set.

A by-subject demographic listing, including the informed consent date, will be provided by subject ID number in ascending order.

5.2. Other Baseline Characteristics

Other baseline characteristics include creatine clearance (as measured by Cockcroft-Gault equation) {[Cockcroft 1976](#)}, height, BMI, body weight, and blood tests. These baseline characteristics will be summarized by treatment sequence and overall using descriptive statistics for continuous variables and using number and percentage of subjects for categorical variables. The summary of baseline characteristics will be provided for the Safety Analysis Set. No formal statistical testing is planned.

A by-subject listing of other baseline characteristics will be provided by subject ID number in ascending order.

5.3. Medical History

General medical history data will be collected at screening and listed only. General medical history data will not be coded.

A by-subject listing of general medical history will be provided by subject ID number in ascending order. The listing will include relevant medical condition or procedure reported term, onset date, ongoing status, and resolution date (if applicable).

6. EFFICACY ANALYSES

Efficacy will not be evaluated in the study.

7. SAFETY ANALYSES

7.1. Adverse Events and Deaths

7.1.1. Adverse Event Dictionary

Clinical and laboratory adverse events (AEs) will be coded using Medical Dictionary for Regulatory Activities (MedDRA) 23.1. System organ class (SOC), high-level group term (HLGT), high-level term (HLT), preferred term (PT), and lower-level term (LLT) will be provided in the AE dataset.

7.1.2. Adverse Event Severity

Adverse events are graded by the investigator using the Common Terminology Criteria for Adverse Events (CTCAE) Toxicity Grading Scale, Version 5. The severity grade of events for which the investigator did not record severity will be categorized as “missing” for tabular summaries and data listings. The missing category will be presented last in the summary presentation.

7.1.3. Relationship of Adverse Events to Study Drug

Study drug related AEs are those for which the investigator selected “Related” on the AE CRF to the question of “Related to Study Treatment.” Relatedness will always default to the investigator’s choice, not that of the medical monitor. Events for which the investigator did not record relationship to study drug will be considered related to study drug for summary purposes. However, by-subject data listings will show the relationship as missing from that captured on the CRF.

7.1.4. Relationship of Adverse Events to Study Procedure

Study procedure related AEs are those for which the investigator selected “Yes” on the AE CRF to the question of “Related to Study Procedures”. Relatedness will always default to the investigator’s choice, not that of the medical monitor. Events for which the investigator did not record relationships to study procedure be considered related to study procedure for summary purposes. However, by-subject data listings will show the relationship as missing from that captured on the CRF.

7.1.5. Serious Adverse Events

Serious adverse events (SAEs) will be identified and captured as SAEs if the AEs met the definition of SAEs that were specified in the study protocol. Serious adverse events captured and stored in the clinical database will be reconciled with the SAE database from the Global Patient Safety Department before database finalization.

7.1.6. Treatment-Emergent Adverse Events

7.1.6.1. Definition of Treatment Emergent

Treatment-emergent adverse events (TEAEs) are defined as any AEs with an onset date on or after the study drug start date and no later than 30 days after permanent discontinuation of study drug. If the AE onset date is the same as the date of study drug start date, the AE onset time must be on or after the study drug start time. If the AE onset time is missing when the start dates are the same, the AE will be considered treatment emergent.

TEAEs with an onset date on/after previous treatment administration date and prior to the next treatment administration date will be attributed to the previous treatment.

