5.5. Fasting and Meals

All study treatments will be administered orally at the study center in the morning at approximately the same time on each day with 240 mL of water following an overnight fast (no food or drink, except water, for at least 10 hours). On non-intensive PK days, participants will continue to fast for 2 hours postdose relative to study drug dosing.

On the days of intensive PK sampling (Days 1, 3, 12, and 14 for Sequence AB and Days 6, 8, 18, and 20 for Sequence BA), the study drug will be administered in the morning following an overnight fast (no food or drink, except water, for at least 10 hours). On intensive PK days, participants will be restricted from food intake until after collection of the 4-hour blood draw. Participants will continue to fast until after collection of the 4-hour PK sample, relative to study drug dosing. Additionally, participants will be restricted from water consumption 1 hour before and until 2 hours after dosing, except for the 240 mL given with the study treatment(s). After collection of the 4-hour PK sample, participants will be provided with a standardized meal.

All meals and/or snacks given to participants during their stay in the clinical study facility will be standardized for all participants and should be similar in calorie and fat content and taken at approximately the same time each day. All meals provided must be approved by the sponsor. Components of meals (eg, margarine, jelly, bread) should be given to participants in individual portions (eg, 1 tablespoon) per the approved meal schedule. The provision of meal components in bulk (eg, a jar of jelly for participants to share) should not be practiced. All meals should be given at approximately the same time each day (eg, 07:30, 12:00, 18:00).

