1.3. Study Design

This study is a Phase 1, randomized, two-way crossover, open-label, single and multiple dose, single center study to evaluate the effect of filgotinib on a mixed OATP/CYP3A, OATP/BCRP, and OATP substrates using phenotypic probes in healthy normal subjects. Up to 30 subjects will be enrolled.

Healthy surgically sterile male and nonpregnant, nonlactating female subjects aged 18 through 55 years old will be enrolled into the study.

Following completion of screening and admission assessments (Day -1), eligible subjects will be randomized at 1:1 ratio on the evening of Day -1 to receive 1 of 2 treatment sequences starting on Day 1. Subjects will dose for 13 days. The treatment end dates are on Day 17 (Sequence AB) or Day 20 (Sequence BA). The completion of assessments is on Day 17 (Sequence AB) or Day 23 (Sequence BA). All subjects will be contacted by telephone 7 (\pm 2) days after last dose for follow up. The treatment schema is shown below in [Figure 1-1](#).

The study drugs and treatments are as follows:

OATP/CYP3A substrate: Atorvastatin (ATV) 40 mg

OATP substrate: Pravastatin (PRA) 40 mg

OATP/BCRP substrate: Rosuvastatin (ROS) 10 mg

Pravastatin/Rosuvastatin (PRA/ROS) will be coadministered as a probe cocktail.

Treatment A: Single dose of ATV 40 mg, followed by a washout period of 1 day and then a single dose of the PRA 40 mg/ROS 10 mg cocktail. All agents should be administered in the morning under fasted conditions.

Treatment B: Filgotinib 200 mg administered once daily for 11 days, with a single dose of ATV 40 mg administered on the sixth day followed by a single dose of PRA 40 mg/ROS 10 mg cocktail administered on the eighth day. All agents should be administered in the morning under fasted conditions.

Table 1-1. Treatment Schema

Sequence	Days									
	Period 1					Period 2				
AB	1	2	3	4-6	7-11	12	13	14	15-17	
	ATV	WO	PRA + ROS	WO	FIL	FIL+ATV	FIL	FIL + PRA + ROS	FIL	
BA	Period 1					Period 2				
	1-5	6	7	8	9-11	12-17	18	19	20	
	FIL	FIL + ATV	FIL	FIL + PRA + ROS	FIL	WO	ATV	WO	PRA + ROS	

FIL = filgotinib; ATV = atorvastatin; PRA = pravastatin; ROS = rosuvastatin; WO=wash out

An overview of the study design is described below and shown in [Figure 1-1](#) and [Figure 1-2](#).

Figure 1-1. Study Schema – Sequence AB

[figure not shown]
[figure not shown]

Figure 1-2. Study Schema – Sequence BA

Pharmacokinetic Assessments

Plasma Pharmacokinetic Collection

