7.1.7. Summaries of Adverse Events and Deaths

The number and percentage of subjects who experienced at least 1 TEAE will be provided and summarized by SOC and PT, and by treatment sequence with treatments listed thereunder based on the Safety Analysis Set as follows:

- All TEAEs
- All TEAEs related to study drug
- All TEAEs related to study procedures
- All TEAEs by severity

- TEAEs of Grade 3 or higher
- All TEAEs related to study drug by severity
- All SAEs
- All SAEs related to study drug
- All TEAEs leading to premature discontinuation of study drug
- Death

There will be two ways to summarize AEs:

- 1) Two treatment sequences will be combined. And the same treatment (FIL, ATV, etc.) from different treatment sequence will be pooled together.
- 2) Two treatment sequences will be summarized separately.

A brief, high-level summary of AEs described above will be provided by the number and percentage of subjects who experienced the above AEs and by treatment group and overall total. All deaths observed in the study will also be included in this summary.

Multiple events will be counted only once per subject per treatment in each summary. An AE that starts in one treatment period and continues into the following treatment period(s) will be counted only in the period in which the AE began. Adverse events will be summarized and listed first in alphabetic order of SOC and then by PT in descending order of total frequency within each SOC, and the alphabetic order of PT will be applied within the same frequency. For summaries by grade, the most severe grade will be used for those AEs that occurred more than once in an individual subject per treatment during the study.

In addition to the above summary tables, all TEAEs and SAEs will be summarized by PT only, in descending order of total frequency and the alphabetic order within the same frequency.

In addition, data listings will be provided by subject for the following:

- All AEs (indicating whether the event is treatment emergent)
- SAEs
- Deaths
- AEs leading to premature discontinuation of study drug

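### SAP 7.1.6.1 attributes TEAEs to treatments by calendar date alone, so an event that starts before the morning dose on a treatment-change date is counted under the new treatment before it is given

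*SAP*

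**What the plan says.** SAP 7.1.6.1 has two paragraphs that do different jobs.

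- The first decides whether an AE is treatment emergent. On the study drug start date it uses the clock: "the AE onset time must be on or after the study drug start time". It also gives a default: "If the AE onset time is missing when the start dates are the same, the AE will be considered treatment emergent".
- The second decides which treatment receives the event. A TEAE with an "onset date on/after previous treatment administration date and prior to the next treatment administration date will be attributed to the previous treatment". No time of day appears.

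SAP 7.1.6.2 (incomplete dates) adds no time rule for attribution. SAP 7.1.7 says that an AE continuing into a later period "will be counted only in the period in which the AE began", which does not place an onset that precedes the dose on a change date. The same section describes one presentation in which "the same treatment (FIL, ATV, etc.) from different treatment sequence will be pooled together", so columns finer than Treatment A versus B are planned.

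Protocol 5.5 states: "All study treatments will be administered orally at the study center in the morning at approximately the same time on each day". No clock hour is given. SAP 1.3 and Table 1-1 set the treatment days; within Treatment B, for example, filgotinib is given daily "with a single dose of ATV 40 mg administered on the sixth day".

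**The concern.** An onset on the date of the next treatment is not prior to that date, so the rule moves the event to the new treatment at any hour. Because dosing is in the morning, every change date has some hours during which the new treatment has not been taken.

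The section also treats like cases differently. An AE at 03:00 on Day 1 is correctly excluded as pre-dose. An AE at 03:00 on Day 7 of Sequence AB is charged to filgotinib, although the first filgotinib dose comes later that morning. The documents give no reason for the difference.

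AE incidence is a named secondary endpoint (SAP 1.2), and the secondary objective concerns filgotinib alone or combined with the probes. At stake is whether the by-treatment AE tables place events on the correct side of a dose. The columns most exposed are FIL+ATV and FIL+PRA+ROS, which under this rule each receive one calendar date per participant.

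**Working it through.** The plan states no figure on this point, so there is none to reproduce. The check has three steps: read the rule literally, list the change dates, and count the pre-dose hours.

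**Inputs.** Treatment days come from SAP Table 1-1. The rule is the second paragraph of SAP 7.1.6.1. Dosing is in the morning (Protocol 5.5); the hour *h* is assumed, with *h* = 7 to 10. Component columns are assumed to follow the labels in Table 1-1, since SAP 7.1.7 gives only examples of the columns.

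**Change dates after Day 1.** Washout days keep the label of the last treatment given.

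| Sequence, day | Label before | Label from this date | Drug added by the new label |
|---|---|---|---|
| AB 3 | ATV | PRA+ROS | PRA, ROS (never taken before) |
| AB 7 | PRA+ROS | FIL | FIL (never taken before) |
| AB 12 | FIL | FIL+ATV | ATV (taken in Period 1) |
| AB 13 | FIL+ATV | FIL | none |
| AB 14 | FIL | FIL+PRA+ROS | PRA, ROS (taken in Period 1) |
| AB 15 | FIL+PRA+ROS | FIL | none |
| BA 6 | FIL | FIL+ATV | ATV (never taken before) |
| BA 7 | FIL+ATV | FIL | none |
| BA 8 | FIL | FIL+PRA+ROS | PRA, ROS (never taken before) |
| BA 9 | FIL+PRA+ROS | FIL | none |
| BA 18 | FIL | ATV | ATV (taken in Period 1) |
| BA 20 | ATV | PRA+ROS | PRA, ROS (taken in Period 1) |

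Each sequence has 6 change dates. On 4 the new label includes a drug not yet given in that period, and on 2 of those 4 the drug has never been taken at all. On the remaining 2 the label drops from filgotinib plus statin to filgotinib alone. With Treatment A/B columns only AB Day 7 and BA Day 18 remain.

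**Share of a change date before the dose** = *h*/24:

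- 7/24 = 29%
- 8/24 = 33%
- 9/24 = 38%
- 10/24 = 42%

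**Hours per participant under the wrong label** = (number of change dates) × *h*. The denominator is the time from the first dose to the last dosing day: (17 − 1) × 24 = 384 h for AB and (20 − 1) × 24 = 456 h for BA.

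- Component columns, *h* = 8: 6 × 8 = 48 h, which is 48/384 = 12.5% (AB) and 48/456 = 10.5% (BA).
- Component columns, *h* = 7 to 10: 42 to 60 h, which is 10.9% to 15.6% (AB) and 9.2% to 13.2% (BA).
- A/B columns, *h* = 7 to 10: 7 to 10 h, which is 7/384 = 1.8% to 10/384 = 2.6% (AB) and 7/456 = 1.5% to 10/456 = 2.2% (BA).

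**One-date columns.** At *h* = 8, FIL+ATV is credited with 8 h before atorvastatin is given and loses the last 8 of the 24 h after it. For any *h* from 7 to 10, an event 18 h after the combined dose starts between 01:00 and 04:00 the next day and goes to FIL alone.

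**With date and time compared**, these misassigned hours fall to zero wherever both times are available.

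**The case against.** The strongest case is that this is a small wording gap in descriptive tables. No decision depends on them: the lack-of-interaction criterion in SAP 8.1.2.2 is purely pharmacokinetic. By-subject AE listings are chronological, and drug-relatedness follows the investigator. The Treatment A versus B contrast is barely touched. On AB Day 7 the error counts against filgotinib and so hides no filgotinib signal. On BA Day 18 a pre-dose event comes almost 7 days after the last filgotinib dose on Day 11. Nor does a time-based rule settle carry-over: an event 25 h after a statin would still go to filgotinib alone, although the protocol gives half-lives of about 14 h for atorvastatin and 19 h for rosuvastatin. All of this stands and limits the weight of the point. It does not make the attribution correct.

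The upper end of the assumed dose range can also be questioned. Protocol 5.5 gives 12:00 as an example mealtime and requires fasting until the 4-hour sample on intensive PK days, which suggests a dose by 08:00 (33%). The same list gives 07:30, which with the 2-hour post-dose fast on other days would mean 05:30 (5.5/24 = 23%). These examples cannot fix the hour, so the range stays an assumption.

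A reader might infer four stronger things that the documents do not support.

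- *Every change date charges an event to a drug never taken.* This is so on 2 of 6 dates per sequence.
- *By-treatment AE incidence is the only safety comparison of statin alone with statin plus filgotinib.* SAP 7.2.2.2 and 7.2.3 also summarize laboratory and liver-related abnormalities by treatment.
- *29% to 42% of AEs are misattributed.* The figure is a share of clock hours on a change date. No AE rate or onset distribution is given.
- *Onset times are known to be recorded for every AE.* This is inferred from the time rules in SAP 7.1.6.1; the eCRF is not among the documents.

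**Conclusion.** The point holds on the literal text. The stated rule places a TEAE that begins before the dose on a change date under a treatment not yet given that day, or detaches it from the filgotinib-plus-statin dose given less than 24 h earlier. This can happen on 6 dates per sequence with component columns and on 1 with Treatment A/B columns.

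The hour-based sizes rest on an assumed 07:00 to 10:00 dose and on columns that follow the Table 1-1 labels. The number of events affected cannot be known from the documents and may be zero. Only the descriptive by-treatment AE tables are affected. Overall TEAE counts and the primary PK analysis are unchanged, and the rule is written for TEAEs, so it does not reach the by-treatment laboratory summaries. It should be corrected because a stated rule gives wrong attributions and the remedy is cheap; it does not threaten the study's main conclusion.

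**What to change.** In the second paragraph of SAP 7.1.6.1, replace the date comparison with date and time. Attribute each TEAE to the treatment most recently administered at its onset, meaning on or after that dose time and before the next treatment's dose time. Keep the present date rule only when the onset time is missing.

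The cost is one sentence and a small derivation change. It depends on onset times being collected for AEs after Day 1, which should be confirmed against the eCRF. Dose times should be confirmed too. SAP 8.1 uses them for the PK analysis, but AB Days 7, 13 and 15 and BA Days 7 and 9 are change dates without a scheduled intensive PK dose. If the SAP is already final, its Introduction provides for documenting the change in the CSR.
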